OVERALL IMPACT, SIGNIFICANCE, INVESTIGATOR(S) & INNOVATION: *inclusion/exclusion criteria not in grant (R1&R2).* We apologize for placing too much of that info in Human Subjects. It is now in section D.2 (and Human Subjects [1.a.]) *Unclear how nonadherence due to smartphone service loss will be handled (R1):* In our feasibility trials we observed high BP monitoring adherence via phone app (~88%), nonadherence tended to occur when cellular service was disrupted. We budgeted for 40% to receive a smart phone or data package to cover phone or service loss during the trial (in D.4.) *Justify relatively limited age range (21-59 yrs) (R1):* We are recruiting AAs from a federally qualified health center (FQHC) with sole diagnosis of HTN (n=2,619; mean age ~45.3 yrs). Majority of those ≥ 60 had multiple comorbidities & JNC8 BP control goals differ for patients <60 vs ≥60. *Concern PI may not have time (25%FTE) to devote to project (R1):* Within 2 mos of start date for this grant, [name] will be covered 50% FTE on grants (R21 & RO1 will have expired; see bio). He has a long track record of running successful concurrent trials. An experienced full time project manager has been added, [name]. *Consider adding someone with usability testing background (R1):* [name] is a consultant with expertise in user centered, iterative design in web/app programs including use of various usability evaluation tactics (e.g., expert heuristic & end user think aloud evals, questionnaires; see bio & letter). *SMASH not highly innovative, been used in other patient groups(R1):* Our patient centered design revealed significant heterogeneity of influence of cultural heritage/acclimation and numeracy of chronic diseases (single vs multi-morbidities) upon MA and other health behaviors within & across ethnic groups. The mHealth program tailored to Hispanics is not culturally attuned for AAs. Our mHealth work with AA renal transplant patients with HTN, diabetes, etc. led to efforts to address poor MA before multi-morbidities develop. Our long-term goal is to prevent common events (e.g., stroke, heart attack) & slow progression of common comorbidities (e.g., chronic kidney disease, diabetes) due to uncontrolled HTN. SMASH for transplant patients required ~2 years of changes to become salient to AAs with solely uncontrolled HTN. We found those with only HTN often have greater MA problems (in C.1.3) & to be more challenging to establish sustained regimen adherence compared to HTNs with multi-morbidities. Experiences during trials & post trial interviews led to an iterative process of identifying highly salient motivational factors (values, beliefs, goals) not needed with multi-morbidity transplant patients (in C.1.5.) Others have observed similar challenges with single vs multi-morbidity HTN patients (in A.2.) This program (nor any earlier iteration) has not been nor is being tested using a fully powered RCT, much less within a low-income population & health system (i.e., FQHC). *No focus on med nonadherence (MNA) mechanisms besides self-motivation or how other diseases & meds affect HTN MA; no lit review on comorbidities(R2):* We clarified HTNs with comorbidities aren't recruited (in D.2.) Exploratory analyses of MNA mechanisms now include med side effects, stress, depression symptoms, etc. (in D.10.) We added diabetes /CVD risk factor changes (e.g., TC, HgA1c) as exploratory outcomes. Recent trials show some newer HTN meds lower or at least do not increase these risk factors (in A.2.) **APPROACH & ENVIRONMENT:** *Limited description of clinics (R1):* 7 of 8 clinics have similar numbers of AAs with uncontrolled HTN and numbers of primary providers (MD, PA, NP; M=2.4). Lead site has 7.3 providers & generates ~45% of patient encounters (in Facilities & Resources). Clinic (=cluster) in our cluster RCT design will be a random effect in the analytic model & account for clinic site differences (in D.10). *More details on SMASH focus group protocol stratification process (R1):* We will identify 2 groups: 16 MA responders & 16 partial/nonresponders stratified by clinic, age & sex. We will run 3-4 focus groups separately by group classification (in D.7.) *Measures of numeracy, usability & project evaluation needed; SMASH & control condition descriptions a bit vague (R1):* We added measures (in D.6.) & reworded SMASH & SC protocols for clarity (in D5-7.) *No model to guide analytic approach; how will data be integrated to provide cohesive story (R1):* We clarified in D.10 our conceptual model is built upon Self-Determination Theory with competence & autonomous motivation as primary MA mediators. We now include socio-demographic (e.g., age, income) & biobehavioral (e.g., med side effects, stress, sleep quality, etc.) factors as potential moderators & mediators of MA. Those results will guide an integrated causal model using structural equation modeling that will identify key active ingredients of SMASH to guide future refinements.

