Responses to the questions were placed into a tree-structured algorithm to generate tailored motivational and positive reinforcement SMS messages that can be delivered automatically. We have expanded the SMS messages used in our last two trials and now have a library of >600 SMS messages. The FQHC and stroke patients who received SMS messages and audio and visual graph feedback also suggested having the VBG questions presented in a web-based app via audio delivery and/or photos, noting that this would easily allow them to refresh their goals over time. We have now done this. An example of branch logic questions on the family domain is presented on a smart phone in Fig 7. (See Appx. 3 for examples of branch logic questions). A common combination of relevant values, beliefs and goals responses involved the belief construct of religiosity in which subjects had strong faith and believed God has a plan for them that included helping their family sustain itself. In the life goals category, their primary short and long-term goals often involved engaging in church activities and spending more time with their grandchildren. Two relevant examples of SMS feedback for a MA score of 1.00 are: "Way to go! Every day of pill taking keeps you on track for...": 1) "many more years watching your grandkids grow up", 2) "attending many more prayer meetings". If one is partially or completely nonadherent, he/she might receive: "Remember taking your pills on time is one way of giving thanks to God for his blessing of life" or "You must have been really busy yesterday. Get back on track taking your pills on time

today and plan some special time with your grandkids". For further examples of personalized messages based on patient responses, see Appx. 4. Positive feedback from SMS messages and phone delivered graphic representations of adherence patterns and BP control over time, intends to increase SMASHer's perceived competence in engaging in the program and link their adherence behaviors with their values, beliefs and goals.

D. Research Design and Methods

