Smashers will complete the values, beliefs and life goals questionnaire (VBG; see Appx. 14). Responses are used in a tree-structured algorithm to select tailored motivational and positive reinforcement SMS or voicemail messages based on previous day’s MA levels. Examples of motivational messaging based upon patients’ responses are provided in C.1.5 and Appx. 4. After 2 consecutive weeks of 100% MA (typically first 2-4 weeks), messages are switched from daily to a variable interval schedule averaging 2 messages/week. Cumulative MA graphs will be sent on their phones weekly during the 6-month trial (MA rate algorithm in Appx. 2). Automated SMS messages will remind subjects to self-measure BP every 3 days. After each BP session, the SMASH app provides audio and visual BP feedback, and opportunity to see BP averages charted over time and against JNC8 guidelines (screenshot example in Appx. 25).

SMASHers will receive 30-45 sec audio or SMS messages 2x/week on HTN facts (e.g., HTN is permanent, uncontrolled HTN is silent killer), importance of timely, consistent MA, tips on expressing questions /concerns with MD (e.g., side effects; examples in Appx. 26). SMASHers will have auto dial feature on their app for [name] (or TACHL service techs if needed) to address technology related issues should they arise.

D.5.b. Provider Level: SMASH primary providers will receive summary reports, designed by them, using patient ID#s every week based upon their preference (e.g., email; NexGen EMR with email reminder to view it; example in Appx. 27). They will receive email reminders for viewing generated reports as needed every 6 hrs for 24hr period. They (and the SC MDs) will receive the same summary charts of JNC8 BP management guidelines used by us in other studies^{22,23,25} (Example in Appx. 28). If a SMASHer’s mean BP exceeds thresholds (e.g., BP >180/ 105 or <100/75 mmHg) during a session, [name] will receive an SMS alert, call the patient and conduct the BP protocol again. If BP still exceeds thresholds, FQHC providers have requested their nurse managers be called to do a follow-up with the patient.

D.5.c. Enhanced Standard Care (SC) Protocol: Subjects whose practice site is randomized to the SC group will continue to use the tray with reminder functions disabled for another 6 months. To **help maximize rigor**

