Exploratory Moderator Analyses: Our conceptual model will guide moderator analyses of MA and BP control using logistic regression with >90% MA or BP control at 6 months as dependent variable and the GLMM/GEE model over the entire study (measurement times 3, 6, 12 and 18 months). Modeling will be carried out in a sequential fashion. Initial set of models will first be adjusted for sociodemographics (age, gender, education, marital status, income), autonomous motivation and biobehavioral factors (e.g., stress, sleep quality, depressive symptoms, med side effects, etc.). If needed, models will be further adjusted for new comorbidities (e.g., diabetes) and associated additional meds. Effect modifications of covariates (moderators) will be examined through inclusion of a covariate-by-group (SMASH vs SC) interaction term in the multivariable models.⁶⁷ We are especially interested in the interaction of treatment by gender, as well as SES and autonomous motivation.

Exploratory MNA Mediation Analyses: Potential mediators will be examined individually and subsequently in a multivariable model. Exploratory analyses will follow modifications suggested by MacKinnon, Fairchild and Fritz¹⁵⁷ of the causal steps approach developed by Baron & Kenny.¹⁵⁸ Analyses will be guided by our conceptual model framed upon change scores in SDT constructs (competence & autonomous motivation) followed by MNA mediators identified in the empirical literature including biobehavioral (e.g. stress, med side effects, depression symptoms, sleep quality, perceived disease severity, doctor-patient relationship, quality of life, HTN knowledge/beliefs) and process /uptake features (e.g., opening of motivational/reinforcement messages/education info, BP graph uploads via phone, patient SMASH (or SC) usability and satisfaction scale

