Description: (The purpose of TSRQ is to assess the degree to which one's motivation for a particular behavior or set of behaviors is relatively autonomous or self-determined, (of if motivation is externally driven (controlled)). The responses on the autonomous items are averaged to form the reflection of autonomous motivation for the target behavior and the responses on the controlled items are averaged to form the reflection of controlled motivation for the target behavior. (In those studies where a motivation has also been assessed, the amotivated responses are also averaged. These three subscale scores can be used separately, or a Relative Autonomy Index can be formed by subtracting the average for the controlled reasons with the average for the autonomous reasons. (Autonomous: (1, 3, 6, 8, 11, 13) (Controlled: (2, 4, 7, 9, 12, 14) (No motivation: (5, 10, 15))

(

((

(

1. Source: (Williams GC et al. (1996) Motivational predictors of weight loss and weight loss maintenance, Journal of Personality and Social Psychology, (70), (115) 26.

(

Sample Characteristics: (94 obese individuals who enrolled in a weight loss program. ((27% male (Mean age 43.4 (Range: (20-77))

(

Psychometric Properties: (Reliability: (Test Retest (coefficient (after 18 months (or more) (Autonomous items: $r = .47$ ($p < .01$), (Controlled items: $.34$ ($p < .05$)).
Validity: (Autonomous items correlated with Autonomy orientation score of General Causality Orientations Scale ($r = .38$, $p < .001$) and the Perceived Autonomy Support of the Health Care Climate Questionnaire ($r = .38$, $p < .001$).
Predictive Value: (Autonomous items at start predicted attendance ($r = .34$, $p < .001$) and BMI ($r = .11$, $p < .05$)).

(

2. Source: (Williams GC et al. (1998) Autonomous regulation and long term medication adherence in adult outpatients, Health Psychology, (17), (269) 276.

(

Sample Characteristics: (126 Adults taking at least one prescription pill ((24.6% male, (mean age 56.3 years, (range: (37-85))

Psychometric Properties: (Reliability: (Internal consistency: (Cronbach's alpha score, (Autonomous items = $.81$, (Controlled items = $.84$)
Validity: (Autonomous items correlated with the Perceived Autonomy Support of the Health Care Climate Questionnaire ($r = .24$, $p < .05$).
Predictive Value: (Autonomous items predicted adherence ($r = .58$, $p < .0005$)).

(

(

Medication Adherence (ASRQ)

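### The exploratory mediation plan sets no time order between the self-determination scores and adherence and does not adjust for earlier adherence, so it cannot tell which drives the other

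*Combined protocol and SAP*

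**What the plan says.** The reply to reviewers in the Introduction to the Revised Application names "competence & autonomous motivation as primary MA mediators" and says the resulting structural equation model will pick out the active components of SMASH for later refinement. Section D.10 gives the method: "Potential mediators will be examined individually and subsequently in a multivariable model", following a modified causal-steps approach, with "Analyses will be guided by our conceptual model framed upon change scores in SDT constructs (competence & autonomous motivation") first. Further candidates follow, including usability and satisfaction scale scores. The results go into exploratory structural equation models of sustained adherence and BP control; no time point is given for sustained.

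On timing, D.6 and Table 3 put the self-determination scales at baseline and months 3, 6, 12 and 18. Tray adherence is daily for 6 months. Patients complete the usability and satisfaction scales only at month 6.

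On the opposite direction, C.1.5 says that positive SMS feedback and "phone delivered graphic representations of adherence patterns and BP control over time" together "intends to increase SMASHer's perceived competence in engaging in the program". D.5.a adds that "Cumulative MA graphs will be sent on their phones weekly during the 6-month trial" and that motivational messages depend on the previous day's adherence. The Aim 2 models in D.10 place adherence among the adjustment variables when the self-determination scores are the outcome.

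**The concern.** Mediation needs the mediator to come before the outcome. Here a patient who adheres well is shown that he does, and this is meant to raise his sense of competence. A higher score may then be a result of adherence, not its cause. If the score change and the adherence change cover the same months, either direction gives the same cross-sectional association, and a causal-steps analysis labels it mediation.

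The plan has no rule that prevents this. For the month-6-only scales the order is wrong by construction when tray adherence is the outcome: the candidate mediator is measured after the 6 months of adherence it is meant to explain.

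At stake is the Aim 3a conclusion about which components work, which feeds SMASH refinement and the next trial. D.12 also gives as an aim of the trial to learn whether lasting improvement results from increased competence and autonomous motivation. That is a causal question.

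**Working it through.** The plan gives no path size, power or sample size for mediation, so there is no figure of its own to reproduce. The check has two parts.

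**1. Order of measurement (D.6, Table 3, D.5.a, D.10).**
- Tray adherence: months 1-6, daily.
- Self-determination change to month 6: spans the same months as the tray outcome, so it has no lead.
- Self-determination change to month 3: could lead tray adherence in months 4-6, but D.10 does not specify this.
- Usability and satisfaction: month 6 only, so no lead over tray adherence is possible.
- Adherence feedback: runs through the whole 6 months.

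**2. What a purely reverse path would produce.** Let adherence be MA = d·G + e, with G the arm and e of variance 1. Let the score be C = r·MA + √(1 − r²)·noise, with no effect of C on MA. Then:
- path a (arm to score) = r·d
- path b (score to adherence, given arm) = r
- apparent proportion mediated = a·b / d = r²

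For r = .20 this is 0.04; for r = .58 it is 0.336. The true value is zero in both cases.

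Inputs: 88 per arm, from the 176 in D.8. The values of r come from the appended scale descriptions: .20 for the self-efficacy scale against electronic monitoring at 3 months, and .58 where "Autonomous items predicted adherence" for the motivation scale. Assumed: d of 0.5, 1 and 2 SD, correlation 0.7 between adherence in the two halves of the trial, no clustering, 2,000 simulated trials per cell, and mediation declared when a and b are both significant at two-sided 0.05.

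| r | d = 0.5 SD | d = 1 SD | d = 2 SD |
|---|---|---|---|
| .20, same period | about 8% | about 19% | about 58% |
| .58, same period | about 49% | about 97% | about 100% |
| either, lagged and adjusted | at most about 5% | at most about 5% | at most about 5% |

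Repeated runs differ by a point or two.

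A second set-up used r from 0.2 to 0.5 and a month-3 to month-6 adherence correlation of 0.6:

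| Model | d = 0.5 SD | d = 1 SD |
|---|---|---|
| Same period | 8% to 38% | 20% to 92% |
| Lagged, not adjusted for earlier adherence | 4% to 36% | 9% to 89% |
| Lagged and adjusted | 0.4% to 1.4% | 1.4% to 4.4% |

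So a lead alone is not enough; the adjustment for earlier adherence does most of the work.

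**Cost of the adjustment.** Now suppose a true early mediator effect acts equally on both halves (slope 0.2, halves correlated 0.7). The lagged, adjusted model detects path b in about 19% of trials, against 74% to 76% without the adjustment.

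**The case against.** **Silence is not a same-period analysis.** A reader might infer that the plan will compute both changes over the same months and so report reverse causation as mediation. No section says that. An ordered reading is possible: the structural model concerns sustained outcomes, all intervention tactics stop at month 6 (D.6), and score change to month 6 could be set against MPR or BP at months 12 and 18. This stands in part. But D.10 does not specify that analysis, it cannot use tray data (which end at month 6), and without adjustment for earlier adherence a lead alone does not protect.

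**The reverse arrow is an aim, and for competence only.** C.1.5 says what the feedback is intended to do, not what it does. Autonomous motivation is promoted by linking adherence to personal values (C.1.2), and no passage says that adherence raises it. This stands.

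**The correlations are borrowed.** Both come from other samples and neither is a within-arm correlation of changes. The appendix also gives .19 for the baseline self-efficacy score with later adherence, close to the concurrent .20. That forward association is unadjusted for earlier adherence, so it does not settle direction, but it is a reason not to assume there is no forward effect. The percentages are illustrations. Reading 34% as the share of motivation's mediation that would be spurious in this trial is unsupported.

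**The error rates depend on the test and the effect size.** Path b alone is falsely significant in about 75% to 77% of trials at .20 and 100% at .58, but mediation also requires path a, so those are not false-mediation rates. D.8 implies standardised adherence effects anywhere from 10/15 = 0.67 SD to 28/6.2 = 4.5 SD, so a range must be shown.

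**The stakes are limited.** The analysis is labelled exploratory, and refinement also draws on focus groups, usability data and provider views. This bears on how much the point matters, not on whether direction can be identified.

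**Conclusion.** The point holds as an identification gap. The plan specifies neither a time order between self-determination change and adherence nor an adjustment for earlier adherence, while its own intervention is designed to make adherence raise competence. It also lists month-6-only scales as mediators of adherence already recorded by then, which goes beyond missing detail. As written, the two directions cannot be told apart, and the exploratory active-ingredients conclusion may be wrong.

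The size is illustrative. If only the reverse path existed, same-period analysis would declare mediation in about 8% to 58% of trials at a correlation of .20 and 49% to 100% at .58, against at most about 5% for the lagged, adjusted model. This rests on the assumed group effects, the assumed stability of adherence, borrowed correlations and no clustering. The documents do not establish that reverse causation will occur or that forward mediation is absent. Primary and secondary efficacy conclusions do not change.

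**What to change.** Keep the planned analysis and pre-specify beside it:

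- **Adherence:** mediator is the baseline-to-month-3 change in each self-determination score; outcome is tray adherence in months 4-6; adjust for arm, baseline mediator and tray adherence in months 1-3.
- **BP:** the same mediator with month-6 BP as outcome, additionally adjusted for month-3 BP.
- **Reverse path:** month 1-3 tray adherence to the month-6 score, adjusted for the month-3 score, reported alongside.
- **Month-6-only scales:** descriptive only in relation to tray adherence.
- **Interpretation rule:** call a construct a driver only if the lagged path supports it.
- **Definition:** state when sustained adherence and BP control are measured in the structural model.

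The cost is analysis-plan wording and analysis time; the month-3 scales and daily tray data are already collected. The plan should state the downside. The lagged, adjusted model has low power for mediation complete before month 3, and D.5.a expects full adherence to be reached within the first weeks. A null lagged result is therefore inconclusive, not evidence against mediation. Residual confounding of mediator and outcome remains in either model.

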(internal validity) we will control for attention exposure by sending SC subjects automated SMS messages on topics related to healthy lifestyle behaviors (diet, physical activity) but not related to MA or HTN functional health literacy. Message length and frequency will be of same length as the personalized messages delivered to SMASHers. To account for time SMASHers measure their BP, the SC subjects will receive, every 3 days, an automated SMS directing them to different 2-3 minute video/YouTube™ clips on healthy lifestyles. For those who prefer hard copy material, brochures (esp. novella format) will be mailed weekly across the 6-month trial (examples of SMS, voice mails, video clip links and brochures can be found in Appx. 29).

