D.6. Measures: Table 3 presents all outcome variables, questionnaires and timing of administration. Most scales have been used with 21-59 yr old AAs and have established psychometrics. We provide brief psychometric information (e.g., internal consistency, test-retest reliability) (see Appx.1, 7-21, for copies and additional psychometrics). We will assess SDT constructs (competence/self-efficacy; MA Self-Efficacy Scale [Appx. 7])^{101,123,124} & autonomous motivation [Treatment Self-Reg. questionnaire; Appx. 8],^{97,125} cultural values, beliefs and life goals,¹⁰⁶ (Appx. 14), self-reported MA (Morisky scale, Appx. 1),^{105,126,127} and MPR (formula in Appx.30).¹²⁸ We will assess sociodemographic, biobehavioral and disease attitudes/knowledge variables which have been identified as potential mediators of MA^{7-10,60-68} including HTN knowledge (Appx. 9),^{129,130} health literacy and numeracy (Test of Functional Health Literacy scale, Appx.10),¹³¹⁻¹³³ med side effects (Appx.11),¹³⁴ quality of life (SF-8, Appx 12),¹³⁵ depression symptoms (Beck Depression Inventory, Appx.13),¹¹³⁻¹¹⁵ stress (Perceived Stress Scale, Appx.15),^{136,137} sleep quality (Pittsburgh Sleep Quality Index; Appx 16),^{138,139} perceived disease severity (Illness Perception Questionnaire, Appx.17),¹⁴⁰ and patient satisfaction with MD (Quality MD/Patient Interaction, Appx.18).¹⁴¹ These questionnaires will be given at baseline and mos 3, 6, 12 and 18. Satisfaction and usability scales will be completed at mo 6 (System Usability Scale, Telemed. Satisfaction and Usability Scale, Mobile App Rating Scale, Appx. 19-21).¹⁴²⁻¹⁴⁷ All intervention tactics cease for both groups at end of 6-mo trial. Follow-up visits will occur at mos 12 and 18. Per SC, all subjects will have blood drawn for bioassays including TC, LDL, HgA1c and blood glucose at baseline, mos 6, 12 and 18.

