scores, mobile app usability scale score). These results will be used in exploratory structural equation modeling with outcomes of sustained MA and BP control. Those findings will further guide SMASH refinement for a future effectiveness RCT. Dropout rate is an important issue. We will assess reasons for dropout and compare groups for missing outcome measures using logistic regression modeling. If >10% of data are missing, we will likely add an intermediate evaluation point in a future RCT to provide more data for use in endpoint imputation. Frequency distributions of adverse events & serious adverse events will also be obtained. Proportions within categories of AEs/SAEs for the SMASH vs. SC will be compared via chi-square analyses.

D.11. Qualitative & Mixed Methods Analyses: As in our other recent studies,¹⁵⁹⁻¹⁶³ we will use the constant comparative method of qualitative analysis derived from constructivist grounded theory.^{164,165} This approach acknowledges researchers' prior knowledge and influence in the process, supports and provides guidelines for building a conceptual framework to understand interrelations (e.g., what and how) between constructs. NVivo 11 will be used to identify common themes constructs regarding MA, BP self-monitoring, etc. Iterative coding will be conducted by [name] to identify thick descriptors of informants' responses, refine theme classifications, and impose a data-derived hierarchy of nodes. Interrelations between individual classifications (e.g., gender, age, responder vs partial/non responder) and themes will be examined for relationships. To evaluate reliability and validity of the conclusions, [name] will code a random selection of 20% of these cases and conduct member checks to ensure validity of the findings. Drs. [name] and [name] will use reflection and a process of immersion and crystallization¹⁶⁶ to reconcile any differences and reach consensus. Once no new themes emerge, thematic saturation will have been reached,¹⁶⁷ We will compare and contrast themes from participants and providers. The quantitative and qualitative data sources will be analyzed in a mixed methods sequential triangulation approach.¹⁶⁸ We will refine SMASH content, delivery format and feedback mechanisms for initial and sustained use, based on participants' adherence data, responses to feedback, providers' responses and other variables that might influence optimal use of SMASH.^{169,170}

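### BP uploads and opening of motivational messages cannot occur in enhanced SC, so the planned two-arm mediation models cannot test them as mediators of SMASH's effect

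*Combined protocol and SAP*

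**What the plan says.** D.10 (Exploratory MNA Mediation Analyses) examines potential mediators singly and then jointly, using a modified causal-steps method. The list starts with change scores in the self-determination constructs, goes on to biobehavioral factors, and ends with "process /uptake features (e.g., opening of motivational/reinforcement messages/education info, BP graph uploads via phone", the "patient SMASH (or SC) usability and satisfaction scale" scores and a "mobile app usability scale score). These results will be used in exploratory structural equation modeling with outcomes of sustained MA and BP control". D.10 adds that the findings will guide refinement of SMASH for a later effectiveness trial.

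D.5.a gives the Bluetooth BP monitor, the SMASH app and the tailored motivational messages to patients at SMASH sites. D.5.c gives "SC subjects automated SMS messages on topics related to healthy lifestyle behaviors", plus links to lifestyle videos to match the time that SMASH patients spend measuring BP. Patients who prefer paper are mailed brochures.

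Table 3 records process/uptake over the first 6 months. D.6 states: "Satisfaction and usability scales will be completed at mo 6". Table 3 assigns those scales to all subjects, and the Human Subjects section (1.b) has SC patients rate their educational materials.

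The plan does not say what value SC patients take on SMASH-only measures, whether those models are restricted to SMASH, or how confounding between mediator and outcome is handled.

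**The concern.** A two-arm mediation analysis needs a mediator that could take a range of values in either arm. BP uploads and opening of motivational messages fail this. Assignment alone determines whether they can occur, so the group-to-mediator path says nothing about a mechanism. The mediator-to-outcome path comes only from SMASH patients, and patients inclined to take their pills are plausibly also inclined to upload readings and open messages. Multiplying the two paths turns that shared disposition into an apparent effect of the programme's component. An inert component could then be credited with the benefit and kept or expanded when SMASH is refined.

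**Working it through.** The plan gives no figure for the mediation analysis, so there is none to reproduce.

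**Inputs from D.8.** 22 patients per clinic × 4 clinics = 88 per arm; ICC 0.04; two-sided 0.05.

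**Assumptions not in the documents.** Continuous outcome with SD 1; uptake in SMASH with mean 0.7 and SD 0.2; SC coded 0; within-arm uptake–outcome correlation r from 0 to 0.5, produced wholly by a prior disposition. Uptake never affects the outcome.

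**Size of the false effect.** Path a (group to mediator) = 0.7 − 0 = 0.7. Uptake is constant in SC, so path b (mediator to outcome, given group) comes from SMASH alone: b = r × 1/0.2. Indirect effect = 0.7 × r/0.2 = 3.5r SD.

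**How often it is significant.** Path a is practically always significant, so the rate is that of the test of b. Residual variance is 1 in SC and 1 − r² in SMASH, averaging 1 − r²/2. Hence z = r√88 / √(1 − r²/2). For r = 0.2, z = 0.2 × 9.38 / 0.990 = 1.90, giving about 47%. For r = 0.3, z = 2.81 / 0.977 = 2.88, giving about 82%.

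**Simulation** (4,000 trials per row, 8 clinics of 22, both paths required to be significant):

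| r | Indirect effect, 3.5r | Simulated indirect effect (SD) | False mediation, SMASH has no effect | Same, total effect must also be significant | True 0.8 SD effect through another component, total effect must be significant |
|---|---|---|---|---|---|
| 0 | 0 | 0.0 | 4.8% | 0.7% | 5.2% |
| 0.1 | 0.35 | 0.36 | 14.5% | 2.1% | 14.9% |
| 0.2 | 0.70 | 0.73 | 46.6% | 6.1% | 44.8% |
| 0.3 | 1.05 | 1.11 | 81.8% | 12.1% | 80.4% |
| 0.5 | 1.75 | 1.83 | 99.9% | 14.1% | 99.1% |

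A repeat simulation gave about 44% at r = 0.2 and 81% at r = 0.3 (fourth column). Across repeats, the total-effect requirement held the rate to about 16% or less when SMASH has no effect.

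In the last column at r = 0.2, the true total effect of 0.80 SD splits into an indirect effect of 0.72 and a direct effect of 0.08. That looks like almost complete mediation by a measure that does nothing.

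**Sensitivity.** The assumed mean changes the size of the false effect far more than its frequency. At r = 0.3, a mean of 0.4 gives 0.4 × 0.3/0.2 = 0.60 SD (simulated 0.61, in 81% of trials). The 88% BP-monitoring adherence reported from the feasibility trials would give 0.88 × 0.3/0.2 = 1.32 SD.

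**SC left missing.** Every patient with data is then in SMASH, group is constant, and path a cannot be estimated.

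**Measures available in both arms.**
- If both arms open their own messages at the same rate, false mediation is 4.9–5.4% and the mean indirect effect is 0.00 SD.
- For a month-6 rating that is itself driven by the outcome (r = 0.3 or 0.5, no total effect), the false effect is only 0.06–0.25 SD. It is significant in 26–29% of trials if the arms differ by 0.2 SD on the rating, and in 88–89% if they differ by 0.5 SD.

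**Baseline adjustment with SC at zero, r = 0.3.** A baseline proxy for the disposition with reliability 0.3, 0.5, 0.8 or 1.0 leaves false mediation at 55%, 35%, 11% or 5%. Adjustment therefore rescues the analysis only if the proxy is nearly perfect.

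**The case against.** Several stronger readings are tempting, and the documents do not support them.

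- **A reader might infer that the usability, satisfaction and app ratings are also absent in SC.** They are not: Table 3, D.10 and the Human Subjects section plan them for both arms. What SC would rate on the mobile app scale is unclear. The real weaknesses are that the arms rate different objects, there is no baseline, and the ratings coincide with month-6 outcomes.
- **A reader might infer that all message opening is SMASH-only.** SC receives its own messages, so a two-arm opening rate could be defined. The plan does not define one. A raw count would also mislead, because D.5.a cuts message frequency after sustained full adherence, so the bias could run in either direction.
- **A reader might infer that the timing is always wrong.** The structural equation model concerns sustained outcomes, and first-6-month uptake and month-6 ratings precede months 12 and 18. The timing objection applies to month-6 outcomes only.
- **A reader might take the Introduction's promise to "identify key active ingredients of SMASH to guide future refinements" as resting on uptake data.** That sentence follows a list of self-determination, sociodemographic and biobehavioral factors. The link from uptake to refinement is in D.10, and focus groups and other data also inform refinement.

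The best defence of the analysis is that causal steps may require a significant total effect, and that with no total effect the offsetting negative direct effect would be visible. This holds when SMASH does nothing. It fails when SMASH works through another component, which is when the search for active ingredients matters. D.10 also does not say whether its modification keeps that requirement. Finally, the correlations and the zero coding are assumed, and the analysis is labelled exploratory. That limits the consequence but does not make the estimate interpretable.

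**Conclusion.** The concern holds for BP uploads and opening of motivational messages. Neither way of handling SC, zero or missing, gives a valid two-arm mediation test. With SC at zero and no true mediation, the false-positive rate is about 5%, 15%, 45% and 80% at correlations of 0, 0.1, 0.2 and 0.3, with mean false effects of about 0, 0.4, 0.7 and 1.1 SD. These figures rest on the assumed uptake distribution, the zero coding, a continuous outcome and a correlation due entirely to confounding. At zero correlation there is no inflation.

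A large false effect should not be claimed for the ratings taken in both arms, where it is smaller. No primary or secondary comparison is affected. The change should be made because it is nearly free and the results are meant to shape the next version of SMASH.

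**What to change.** In D.10:

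1. Remove BP uploads and opening of motivational/reinforcement messages from the two-arm mediator models and the structural equation model. Report them as engagement–response associations within SMASH, labelled non-causal.
2. Keep message opening as a two-arm mediator only if it is defined as the proportion of delivered messages opened in each arm, with a stated rule for SC patients who receive mailed brochures.
3. Treat the month-6 usability, satisfaction and app ratings as descriptive for month-6 outcomes, and state what SC rates on each scale.
4. Base mediation on constructs measured in both arms at baseline and month 3 (the self-determination scales, side effects, stress, sleep, illness perception), adjusted for baseline. Use them to explain later outcomes: tray adherence in months 4–6, and BP at month 6 or later. A cumulative 6-month adherence score would not do, because it includes the months before the mediator is measured.
5. State whether a significant total effect is required and how the indirect effect is tested. Acknowledge that some mediator–outcome confounding will remain.

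The cost is analysis-plan wording, since the month-3 measures are already scheduled. The downside is that SMASH-only engagement can no longer be called a mediator.
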